### 12.3 DEATHS

Information for all subjects who die during the study period from randomization to the end of study (including 30 days after the last study drug dosing) will be listed. The number and percent of subjects who die will be summarized by treatment group.

In addition, the information for vital status, including alive/death, last known date subject is alive, or date of death at the study closure, will also be listed.

Death information is also analysed as an efficacy endpoint as described in Sections [10.1.1.2](#) and [10.1.1.3](#).

### 12.4 PREGNANCIES

Pregnancy test results for female subjects will be listed.

### 12.5 CLINICAL LABORATORY EVALUATIONS

Blood samples will be taken at Baseline; Weeks 12, 24, 36; and every 24 weeks thereafter during the study. All samples will be sent to a central laboratory for evaluation of clinical chemistry and hematology. Urine samples collected at screening and study drug termination visit will be collected and sent to a central laboratory for urinalysis.

#### 12.5.1 *Clinical Chemistry*

The following clinical chemistry parameters will be evaluated by the central laboratory:

Parameter	Units
Sodium	mmol/L
Potassium	mmol/L
Chloride	mmol/L
Bicarbonate	mmol/L

Parameter	Units
Albumin	g/L
Blood urea nitrogen (BUN)	mmol/dL
Total bilirubin	umol/dL
Indirect bilirubin	umol/dL
Direct bilirubin	umol/dL
Alkaline phosphatase	U/L
Alanine aminotransferase (ALT/SGPT)	U/L
Aspartate aminotransferase (AST/SGOT)	U/L
Gamma-glutamyl transferase (GGT)	U/L
Creatinine	umol/L
Thyroid stimulating hormone (TSH)	mIU/L
Thyroxine (T4; free)	pmol/L

Values that are “high” or “low” with respect to the reference range provided by the central laboratory will be flagged with an “H” or an “L.” All parameters will be listed for all subjects and assessments, along with their respective “high/low” flags.

Values of these parameters at each assessment and their corresponding changes from Baseline will be descriptively summarized by treatment group.

For each parameter, the frequency and percentage of subjects within each treatment group who had “low,” “normal,” or “high” Baseline values, then subsequently had “low,” “normal,” or “high” follow-up values at each assessment will be presented in a shift summary.

### ***12.5.2 Hematology***

The following hematology parameters will be evaluated by the central laboratory:

Parameter	Units
Red blood cell (RBC) count	$10^6/\mu\text{L}$
Hemoglobin	g/dL
Hematocrit	%
Platelet count	$10^3/\mu\text{L}$
White blood cell (WBC) count	$10^3/\mu\text{L}$

Values that are “high” or “low” with respect to the reference range provided by the central laboratory will be flagged with an “H” or an “L.” All parameters will be listed for all subjects and assessments, along with their respective “high/low” flags.

Values of these parameters at each assessment, and their corresponding changes from Baseline will be descriptively summarized by treatment group.

For each parameter, the frequency and percentage of subjects within each treatment group who had “low,” “normal,” or “high” Baseline values, then subsequently had “low,” “normal,” or “high” follow-up values at each assessment will be presented in a shift summary.

### **12.5.3 Urinalysis**

All urinalysis information will be listed for all subjects and assessments. The presence of protein and blood in the urine will be categorically summarized by treatment group.

## **12.6 ELECTROCARDIOGRAMS**

All ECG assessments will be listed for all subjects. This listing will include the heart rate, QT interval, QTc interval (calculated using formulas by both Bazett and Fridericia as described in Section 8.5), PR interval, QRS duration, whether there were clinically significant changes from Screening visit, whether abnormalities were present, and details and comments on any abnormalities. The ECG results at each assessment and changes at Week 24 will be descriptively summarized by treatment group. In addition, for QTc interval calculated using both the Bazett and Fridericia methods, the number and percent of subjects with values  $\geq 500$  msec and the number and percent of subjects with changes of  $< 30$  msec, 30 to  $< 60$  msec, and  $\geq 60$  msec will be presented by treatment group.

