1.2.4 Efficacy and Safety Data

UT-15C has previously been evaluated in three randomized, placebo-controlled Phase 3 studies (TDE-PH-301, TDE-PH-302, and TDE-PH-308). Additionally, subjects completing these studies have been provided long-term access to UT-15C in an open-label extension study (TDE-PH-304). To date, over 1000 PAH patients have been exposed to study drug (UT-15C or placebo) in the TDE-PH-301, TDE-PH-302, and TDE-PH-308 studies and over 890 patients have received UT-15C in the open-label extension study.

TDE-PH-301 was a 16-week, randomized, double-blind, placebo-controlled, international Phase 3 efficacy and safety study of treprostinil diethanolamine (UT-15C), in patients with PAH. Patients received UT-15C or placebo BID in combination with an ERA, a PDE5-I, or both. The primary endpoint was placebo-corrected change in 6MWD from Baseline to Week 16. Secondary endpoints included Borg dyspnea score, dyspnea-fatigue index, WHO Functional Class, and time to clinical worsening. Study drug dose was titrated up to a maximum of 16 mg BID based on clinical response and study drug tolerability.

Three-hundred fifty-four subjects were enrolled with 30% receiving an ERA alone, 25% a PDE5-I alone, and 45% both agents. The population was 81% female, predominantly WHO Functional Class III (76%), and had a mean baseline 6MWD of 346 m. PAH etiology included idiopathic or heritable PAH (66%), or PAH associated with CTD (26%), repaired congenital systemic-to-pulmonary shunt (7%), or HIV infection (1%). There were no remarkable demographic differences between treatment groups.

Twenty-two percent of subjects discontinued UT-15C therapy compared to 14% in the placebo group. The primary reason for discontinuation was AEs: 14% in the UT-15C group compared to 5% in placebo. There were three deaths in each of the treatment groups.

The Hodges-Lehmann (H-L) estimate of 6MWD placebo corrected median change from baseline at Week 16 was +11 m ($p=0.072$). The change in 6MWD was significant at Week 12 (+13 m, $p=0.015$). The lack of significance at Week 16 may be attributable to the number of subjects who did not provide an efficacy measure at Week 16 due to discontinuing from the study prematurely.

Secondary endpoints of the combined 6MWD and Borg dyspnea score and the dyspnea-fatigue index demonstrated statistically significant changes at Week 16 for UT-15C compared to Baseline ($p=0.013$ and 0.01 , respectively).

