TDE-PH-304 is a long-term, open-label, international, Phase 3 study designed to provide access to UT-15C for subjects previously enrolled in studies TDE-PH-301, TDE-PH-302, TDE-PH-308, or other specified studies conducted during the UT-15C development program. Secondary objectives of the study are to assess the long-term safety of UT-15C in PAH patients and to assess the effect of continued therapy on exercise capacity via 6MWD following one year of treatment with UT-15C. As of 01 September 2015, over 896 subjects were enrolled, representing 2377.7 patient-years of exposure. The mean and maximum duration of exposure was 138.8 and 444.9 weeks (2.66 and 8.53 years), respectively. The mean dose of oral treprostinil achieved was 3.9, 4.5, 4.8, 5.0, 5.5, 5.9, and 5.9 mg BID at 1 year (N=605), 2 years (N=472), 3 years (N=337), 4 years (N=230), 5 years (N=119), 6 years (N=77), and 7 years (N=37), respectively. AEs were typical of PGI₂ therapy; laboratory

findings were unremarkable and did not suggest any specific safety concerns related to long-term treatment with UT-15C. Following 12 months of oral treprostinil treatment, the mean 6MWD increased by +25 meters as compared with Baseline. Kaplan-Meier analysis of subject survival demonstrated 1-, 2-, and 3-year survival estimates of approximately 93.6%, 87.9%, and 82.2%, respectively.

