3.2.2.4 Adverse Events

AEs will be captured from the time the ICF is signed. All AEs should be followed until either resolution (or return to normal or Baseline values), until they are judged by the Investigator to no longer be clinically significant, or for up to 30 days if the AE extends beyond the final visit. All SAEs should be followed until resolution, death, or the subject is lost to follow-up even if they are ongoing more than 30 days after completion of the final visit. Sections 9 and 15.4 provide the guidelines and definitions for recording AEs.

Symptoms of PAH (disease related events) should only be recorded as an AE if the event is either serious, new, or unusual with respect to intensity, frequency, duration as compared to symptoms in the subject's medical history; or there is a reasonable possibility that the event was caused by the study drug.

3.2.2.5 12-Lead ECG

Twelve-lead ECGs will be recorded after at least 5 minutes rest in the semi-recumbent position at Screening, Week 24, and at the Study Drug Termination Visit. Recordings should include lead II as a rhythm strip and contain at least five QRS complexes. ECG parameters collected include heart rate, PR interval, QT interval, QRS duration, and any clinically significant abnormalities.

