## 8 GENERAL CONSIDERATIONS FOR DATA ANALYSES

All the data collected in the electronic Case Report Form (eCRF) will be listed. In general, listings will be sorted by treatment group, subject number, and scheduled assessment (if applicable). Listings will include assessment date, assessment time (if available), study day, and all relevant data collected in the eCRFs. For data collected on a fixed schedule, the assessment identifier will also be included on the listing. Repeat or redundant observations within an assessment window and observations that do not fall within any predefined assessment window (and will, therefore, be excluded from summaries) will be flagged in these listings. Subjects who will not be included in the analysis population (eg, Safety Population, Per-protocol Population) will be flagged.

In general, the data will be summarized by scheduled assessment (if applicable) within each treatment group. For continuous variables, summary statistics will include the mean, standard

deviation, median, minimum, and maximum. For summaries of non-normal data, such as 6MWD, interquartile range (lower quartile, upper quartile) may also be included. Minimums and maximums will be expressed using the level of precision in which the variable was collected. All other statistics will be rounded, using an additional decimal place than was collected. For discrete variables, summaries will include the frequency and percentage in each category. Percentages will be rounded to 1 decimal place. For all inferential analyses and descriptive comparisons, p-values will be rounded to 4 decimal places. Values less than 0.0001 will be denoted as  $<0.0001$ , and values greater than 0.9999 will be denoted as  $>0.9999$ . Wherever practical, categories of discrete variables will be ordered and labelled as they appear in the eCRF.

All analyses are performed using the statistical software SAS® (SAS Institute 2015).

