**Table 8-1 Assessment Windows for Scheduled Visits**

Visit	Target Study Day	Study Day Interval
ECGs and hemodynamics:		
Baseline	1	Study Day $\leq 1$ (prior to the first dose)
Week 24	169	$148 \leq$ Study Day $\leq 190$
Clinical laboratory assessments and NT-proBNP:		
Baseline	1	Study Day $\leq 1$ (prior to the first dose)
Week 12	85	$2 <$ Study Day $\leq 127$
Week 24	169	$127 <$ Study Day $\leq 211$
Week 36	253	$211 <$ Study Day $\leq 337$
Week 60	421	$337 <$ Study Day $\leq 505$
Weeks 84, 108, etc	589, 757, etc	(Target Study Day $\pm 84$ days)
6MWT, WHO FC, and vital signs:		
Baseline	1	Study Day $\leq 1$ (prior to the first dose)
Week 4	29	$15 \leq$ Study Day $\leq 43$
Week 8	57	$43 <$ Study Day $\leq 71$
Week 12	85	$71 <$ Study Day $\leq 127$
Week 24	169	$127 <$ Study Day $\leq 211$
Week 36	253	$211 <$ Study Day $\leq 295$
Weeks 48, 60, etc	337, 421, etc	(Target Study Day $\pm 42$ days)

Note: Study Day = (Assessment Date) - (First Dosing Date) + 1

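### As written, the SAP leaves the protocol-required Study Drug Termination ECGs out of the change-from-baseline summary and, on the most natural reading, out of the QTc category counts.

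*SAP*

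**What the plan says.** ECG is a safety objective in both documents (Protocol 2.2, SAP 2.3). Protocol 3.2.2.5 schedules 12-lead ECGs "at Screening, Week 24, and at the Study Drug Termination Visit", and Protocol 7.4 places the termination assessments at the decision to stop drug, before down-titration.

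Four SAP provisions bear on how these ECGs are analysed:

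- Section 3 describes ECGs at Screening and Week 24 only. It does not mention the termination ECG.
- Table 8-1, under "ECGs and hemodynamics", has two rows: Baseline, and Week 24 with target Day 169 and Days 148–190.
- Section 8 says that "observations that do not fall within any predefined assessment window (and will, therefore, be excluded from summaries) will be flagged in these listings".
- Section 12.6 lists every ECG. For summaries it says "The ECG results at each assessment and changes at Week 24 will be descriptively summarized by treatment group". It then asks for counts of QTc at or above 500 msec and for three categories of QTc change, with no visit named.

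**The concern.** Read together, these rules give a termination ECG no place in the summaries unless it falls inside one six-week interval. Other safety data are treated differently. Laboratory and vital-sign windows in Table 8-1 run on after Week 24 without an end, and SAP 12.7 summarises vital-sign changes at every post-baseline assessment. ECGs share their single isolated window only with hemodynamics, which have no termination measurement to lose.

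What is at stake is the content of the QTc table (Table 14.3.6.2). If only windowed ECGs count, it describes subjects who had an ECG near Week 24. It omits the on-drug ECG taken when a subject stops, whether early or long after Week 24. If unwindowed ECGs do count, the SAP does not say which value represents a subject who has both a Week 24 and a termination ECG. Section 8.6.2 chooses only among observations within one window. Two programmers could produce different tables from the same data.

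**Working it through.** **1. The window.** Week 24 target: 24 × 7 + 1 = Day 169. 169 ± 21 gives Days 148 to 190, 43 days in all. This reproduces Table 8-1.

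**2. The planning rates.** Medians of 32 months (placebo) and 51 months (UT-15C) come from Protocol 10.2 and SAP 5. Under exponential times, the Month 12 event rate is 1 − exp(−12 ln2/32) = 22.9% and 1 − exp(−12 ln2/51) = 15.0%. The plan states 23% and 15%.

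**3. Inputs for exit times.** Accrual takes 3 years, with 10% dropout (Protocol 10.2, SAP 5). The study lasts 4 years (Protocol 3.5). I assume uniform entry, 1:1 allocation, exponential dropout set to reach 10% in each arm, 30.4375 days per month, and one termination visit per subject at exit.

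**4. Daily hazards.**

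- Worsening: ln2/(32 × 30.4375) = 0.000712 (placebo) and ln2/(51 × 30.4375) = 0.000447 (UT-15C).
- Dropout hazards that give 10% overall: 0.000164 and 0.000145.
- Total h: 0.000876 and 0.000592.

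**5. Shares of termination visits.** The last subject enters one year before the end, so through Day 190 only these two hazards act.

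| | Formula | Placebo | UT-15C | Both |
|---|---|---|---|---|
| Before Day 148 | 1 − exp(−147h) | 12.1% | 8.3% | 10.2% |
| Days 148–190 | exp(−147h) − exp(−190h) | 3.2% | 2.3% | 2.8% |
| After Day 190 | exp(−190h) | 84.7% | 89.4% | 87.0% |
| Outside window | 1 − middle row | 96.8% | 97.7% | 97.2% |

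A simulation with the same inputs gives the same shares.

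**6. Range.** With dropout assumed at 25% the share outside is 96.3%, and at 40% it is 95.3%. Protocol 10.2 also allows enrolment to continue until about 190 reported events, so some subjects could have short follow-up. Spreading entry over 46 of the 48 months, with 10% dropout, multiplies in-study survival at day t by (48 − t/30.4375)/46, capped at 1. That gives about 16% before Day 148, 5% inside and 79% after, so about 95% outside.

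**7. Off-drug versus on-drug.** Protocol 7.4 asks that subjects who stop drug before Week 24 for reasons other than worsening be encouraged to keep attending through Week 24, where an ECG is due. Table 8-1 sets no on-treatment condition for ECGs, whereas SAP 10.2.1 excludes walk distances obtained after drug termination from the rank analysis. Such a subject's off-drug Week 24 ECG could therefore enter the table while the same subject's on-drug termination ECG does not.

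**The case against.** The strongest reply is that SAP 12.6 does not clearly exclude these ECGs. It summarises results at each assessment, its QTc counts name no visit, and SAP 8.6.1 applies windows to data summarised by scheduled visit, which a per-subject count need not be. This stands in part: exclusion from the QTc counts is an inference. It does not rescue the change summary, which is limited to Week 24. Nor does it supply a termination or any-post-baseline category, or a rule for subjects with several ECGs. It is also true that every ECG is listed with its abnormalities, so no data are lost, and that no efficacy, alpha or sample-size result depends on this.

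The contrast with laboratory and vital-sign data has a limit too. Under SAP 8.6.2 a termination value can be displaced by another observation closer to the target day.

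Several stronger readings are tempting but not supported:

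- **All early stoppers lack a post-baseline ECG.** Subjects stopping for reasons other than worsening may attend Week 24 and have one, off drug.
- **About one in five UT-15C subjects would be missing, unequally by arm.** A reader might infer this from TDE-PH-301: "Twenty-two percent of subjects discontinued UT-15C therapy compared to 14% in the placebo group". That trial dosed BID and began at 1 mg (Protocol 1.2.4). This one starts at 0.125 mg TID and plans for 10% dropout.
- **The omitted later ECGs are at higher doses.** A reader might cite the open-label study: "The mean dose of oral treprostinil achieved was 3.9, 4.5, 4.8, 5.0, 5.5, 5.9, and 5.9 mg BID". That is 7.8 to 11.8 mg per day, below the Week 24 goal range in Protocol Table 6-1 (5.5–6.5 mg TID, or 16.5–19.5 mg per day). The 12 mg TID maximum is a ceiling and does not predict the dose reached.
- **The chance of a worsening event in Days 148–190 measures the loss.** That is a share of subjects, and it ignores exits by dropout and at study end.

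**Conclusion.** The point holds as a gap in the summaries. The stated rules remove nearly all termination ECGs from the change-from-baseline summary. They also leave the QTc counts either restricted to the Week 24 window, which is the more natural reading, or undefined.

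The size is about 97% of termination visits outside the window under the plan's own inputs, and about 95–96% under higher assumed dropout. This is a planning estimate and not a figure in the documents. It rests on exponential times and on every exit producing a termination visit; deaths and losses to follow-up would yield no ECG. The documents do not show that the omitted ECGs would change the QTc conclusion, or in which direction. The change should be made because the existing rules would produce a less informative safety table from data already collected.

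**What to change.** 1. Add a row to Table 8-1 for ECGs, Study Drug Termination / last on-treatment, and summarise its change from baseline alongside Week 24.
2. In SAP 12.6, base the counts of QTc at or above 500 msec and of the change categories on each subject's worst post-baseline on-treatment ECG from any visit.
3. Keep the Week 24 summary, and state whether ECGs taken after drug has stopped may enter it.
4. Correct SAP 3 so that it lists the termination ECG.

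The cost is SAP wording and an extra table column; no new data are needed. The drawback is that termination ECGs come at varying times, so the new row is not a fixed-time comparison between arms and should be labelled accordingly.

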## **12.7 VITAL SIGNS**

All vital sign assessments will be listed for all subjects. This listing will include weight, heart rate, systolic and diastolic blood pressure, and respiration rate. The vital sign results at each assessment and changes for each post-Baseline assessment will be descriptively summarized by treatment group.

### **12.8 DISEASE-RELATED EVENTS**

All disease-related events occurring during the study will be listed for all subjects. Overall frequency of each type of event will be summarized by treatment group.

### **13 PHARMACOKINETICS**

No pharmacokinetic measures will be assessed in this study.

**15 APPENDICES****15.1 INCLUSION AND EXCLUSION CRITERIA**

A subject is eligible for inclusion in this study if all of the following criteria apply:

1. The subject voluntarily gives informed consent to participate in the study.
2. The subject is 18 to 75 years of age (inclusive) at Screening (ie, date of providing written informed consent).
3. Women of childbearing potential (WOCBP) include any female who has experienced menarche and who has not undergone successful surgical sterilization (hysterectomy, bilateral tubal ligation or bilateral oophorectomy) or is not postmenopausal (defined as amenorrhea for at least 12 consecutive months). Women of childbearing potential must practice true abstinence from intercourse when it is in line with their preferred and usual lifestyle, or use 2 different forms of highly effective contraception for the duration of the study and for at least 30 days after discontinuing study medication. Medically acceptable forms of effective contraception include: (1) approved hormonal contraceptives (such as birth control pills), (2) barrier methods (such as a condom or diaphragm) used with a spermicide, (3) an intrauterine device (IUD), or (4) partner vasectomy. For women of childbearing potential, a negative urine pregnancy test is required at Screening and Baseline prior to initiating study medication.
4. The subject, if male, must use a condom during the length of the study, and for at least 48 hours after discontinuing study medication.
5. The subject has a diagnosis of symptomatic idiopathic or heritable PAH, PAH associated with connective tissue disorder (CTD), PAH associated with human immunodeficiency virus (HIV) infection, PAH associated with repaired congenital systemic-to-pulmonary shunt (at least 1 year since repair with respect to the date of providing informed consent), or PAH associated with appetite suppressant or toxin use.
6. The subject, if known to be positive for HIV infection, has a CD4 lymphocyte count of at least 200 cells/mm^3 assessed at Screening and is receiving current standard of care anti-retroviral or other effective medication for treatment of HIV infection.
7. The subject must have a Baseline 6MWD greater than or equal to 150 meters, in the absence of a concurrent injury, illness (other than PAH or a PAH related condition), or other confounding factor including, but not limited to, use of an aid for ambulation (eg, use of a cane or walker) or connection to a non-portable machine, that would prevent the accurate assessment of the subject's exercise capacity.
8. The subject must be optimally treated with conventional pulmonary hypertension therapy (eg, oral vasodilators, oxygen, digoxin, diuretics, anticoagulants as deemed appropriate by the Investigator) with no additions, discontinuations, or dose changes for a minimum of 10 days prior to randomization. The exceptions are the discontinuation or dose changes of anticoagulants and/or dose change of diuretics.

9. The subject must have been receiving a PAH-approved oral monotherapy at a minimum dose that complies with the approved prescribing information for the product for at least 30 days prior to randomization and must have been receiving a stable dose for at least 10 days prior to randomization. The subject who previously received 2 PAH-approved oral therapies at the same time (specifically, a PDE5-I, an ERA, or an sGC stimulator) will be eligible provided they received these medications concomitantly for less than or equal to 90 days cumulatively. The subject must have taken only 1 PAH-approved therapy for at least 30 days prior to randomization and must have been receiving a stable dose for at least 10 days prior to randomization.
10. The subject has previously undergone a cardiac catheterization within 3 years prior to the start of Screening, or during the Screening period, and the most recent assessment has documented a PAPm of at least 25 mmHg, a PCWP (or in the event a PCWP cannot be reliably obtained, a left ventricular end-diastolic pressure [LVEDP]) less than or equal to 15 mmHg, and absence of unrepaired congenital heart disease (other than patent foramen ovale [PFO]). In the event that a reliable PCWP or LVEDP is unobtainable during cardiac catheterization, subjects with clinically normal left heart function and absence of clinically relevant mitral valve disease on echocardiography are eligible for enrollment.
11. The subject has undergone echocardiography with evidence of clinically normal left systolic and diastolic ventricular function and absence of any clinically significant left sided heart disease (eg, mitral valve disease). Subjects with clinically insignificant left ventricular diastolic dysfunction due to the effects of right ventricular overload (ie, right ventricular hypertrophy and/or dilatation) are eligible.
12. The subject has a previous ventilation perfusion lung scan, and/or high resolution computerized tomography scan of the chest, and/or pulmonary angiography that are consistent with the diagnosis of PAH (eg, low probability of pulmonary embolism; absence of major perfusion defects).
13. The subject has pulmonary function tests conducted within 6 months before Screening or during the Screening period to confirm the following:
  - a. Total lung capacity (TLC) is at least 60% (predicted value) assessed by either whole body plethysmography or helium dilution or nitrogen washout technique
  - b. Forced expiratory volume at 1 second (FEV1) of at least 50% (predicted value)
14. In the opinion of the Principal Investigator, the subject is able to communicate effectively with study personnel, and is considered reliable, willing, and likely to be cooperative with protocol requirements, including attending all study visits.

A subject is not eligible for inclusion in this study if any of the following criteria apply:

1. The subject is pregnant or lactating.
2. The subject has previously received UT-15C.
3. The subject has received a prostacyclin (except if used during acute vasoreactivity testing) within 30 days prior to randomization or had previous intolerance or

significant lack of efficacy to any prostacyclin or prostacyclin analogue that resulted in discontinuation or inability to titrate that therapy effectively.

4. The subject has had any background conventional therapies for PAH added, removed, or dose adjusted (including but not limited to oxygen, vasodilators, diuretics, digoxin, anticoagulants) within 10 days prior to randomization. The exceptions are removal or dose adjustments of anticoagulants and/or dose adjustments of diuretics.
5. The subject has received their first dose of a PAH-approved therapy less than 30 days prior to randomization, has had their PAH-approved oral monotherapy dose changed within 10 days prior to randomization, the subject discontinued any PAH-approved therapy within 30 days prior to Screening, or the subject previously received 2 PAH approved oral therapies (specifically, a PDE5-I, an ERA, or an sGC stimulator) concomitantly for more than 90 days cumulatively.
6. The subject has any disease associated with PAH other than CTD, HIV infection, repaired (for at least 1 year) congenital systemic-to-pulmonary shunt, PAH associated with appetite suppressant/toxin use (eg, portal hypertension, chronic thromboembolic disease, pulmonary veno-occlusive disease, etc), or has had an atrial septostomy.
7. The subject has a current diagnosis of uncontrolled sleep apnea as defined by their physician.
8. The subject has a history of ischemic heart disease, including a previous myocardial infarction or symptomatic coronary artery disease within 6 months prior to Screening or a history of left sided myocardial disease as evidenced by a mean PCWP (or a LVEDP) greater than 15 mmHg or left ventricular ejection fraction less than 40%, as assessed by either multigated angiogram (MUGA), angiography, or echocardiography.
9. The subject has uncontrolled systemic hypertension, as evidenced by systolic blood pressure greater than 160 mmHg or diastolic blood pressure greater than 100 mmHg.
10. The subject has ALT or AST levels at least greater than 3 times the upper limit of normal, clinically significant liver disease/dysfunction, or known Child-Pugh Class C hepatic disease at Screening.
11. The subject has any other disease or condition that would interfere with the interpretation of study assessments.
12. The subject has a musculoskeletal disorder (eg, arthritis affecting the lower limbs, recent hip or knee joint replacement, artificial leg), is using a device to assist walking (eg, cane or walker), or any disease that is likely to limit ambulation, or is connected to a machine that is not portable.
13. The subject has an unstable psychiatric condition or is mentally incapable of understanding the objectives, nature, or consequences of the study, or has any condition which in the Investigator's opinion would constitute an unacceptable risk to the subject's safety.
14. The subject is receiving an investigational drug, has an investigational device in place, or has participated in an investigational drug or device study within 30 days prior to Screening.
15. The subject has chronic renal insufficiency, as defined by either a Screening creatinine value greater than 2.5 mg/dL (221 µmol/L) or the requirement for dialysis.

16. Subjects must not have 3 or more of the following left ventricular disease/dysfunction risk factors:
- i. Body Mass Index (BMI)  $\geq 30$  kg/m^2
  - ii. History of essential hypertension
  - iii. Diabetes mellitus (any type)
  - iv. Historical evidence of significant coronary disease established by any one of the following: history of myocardial infarction or percutaneous coronary intervention or angiographic evidence of coronary artery disease (>50% stenosis in at least 1 coronary artery), positive stress test with imaging, previous coronary artery bypass graft, stable angina

